## **8.4 Final Study Visit**

### **8.4.1 Visit 23, Study Day 750±14, Day 722 (24 months) Clinic Visit Following Second Vaccination**

- Obtain interim medical history, including an assessment for new medical conditions by interview of subjects and note any changes since the previous clinic or phone visit.

- Ask about febrile/rash illness. If the subject reports history of AFI/ARI within the past 14 days, conduct a febrile/rash illness assessment and sample collection as per [Section 8.7](#).
- A targeted physical examination will be performed, if indicated based on review of complete medical history.
- Collect blood samples for humoral immunity and CPT tubes.
- Any unsolicited SAEs, AESIs, and new onset chronic medical conditions will be assessed and recorded on the appropriate case report form.

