## **9.4 Type and Duration of Follow-up of Adverse Events**

Solicited injection site and systemic AEs (reactogenicity events) will be documented and reported from Day 1 through Day 8 after each study vaccination via memory aid, clinic visits on Day 2 and Day 8 after vaccination, and interview by telephone visit on Day 4 after each study vaccination.

Unsolicited AE will be documented from Day 1 through approximately 28 days after the last vaccination. Blood for safety laboratory tests will be collected on Day 8 and Day 15 after each study vaccination. All AEs will be assessed and followed through resolution or stabilization even if this extends beyond the study-reporting period.

AEs related to AFI/ARI will be collected and assessed from the time the ICF is signed through the end of the study, and followed until resolution or stabilization.

SAE, AESIs, and new-onset chronic medical conditions will be collected and assessed from the time of the first study vaccination through the end of the study, and followed until resolution or stabilization. Resolution of an AE and SAE is defined as the return to pretreatment status or stabilization of the condition with the expectation that it will remain chronic.

AFI and ARI will be collected after signing ICF through the end of the study.

Follow-up procedures, evaluations, and outcomes will be recorded on the appropriate case report form.

---

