1. PREFACE

This Statistical Analysis Plan (SAP) for DMID Protocol 16-0034, “*Phase I, Randomized, Double-blinded, Placebo-Controlled Dose De-escalation Study to Evaluate the Safety and Immunogenicity of Alum Adjuvanted Zika Virus Purified Inactivated Vaccine (ZPIV) Administered by the Intramuscular Route in adult Subjects Who Reside in a Flavivirus Endemic Area*

” describes and expands upon the statistical information presented in the protocol.

This document describes all planned analyses and provides reasons and justifications for these analyses. It also includes sample tables, listings, and figures planned for the final analyses. Regarding the final analyses and Clinical Study Report (CSR), this SAP follows the International Conference on Harmonisation of Technical Requirements for Registration of Pharmaceuticals for Human Use (ICH) Guidelines, as indicated in Topic E3 (Structure and Content of Clinical Study Reports), and more generally is consistent with Topic E8 (General Considerations for Clinical Trials) and Topic E9 (Statistical Principles for Clinical Trials). The structure and content of the SAP provides sufficient detail to meet the requirements identified by the FDA and ICH, while all work planned and reported for this SAP will follow internationally accepted guidelines published by the American Statistical Association and the Royal Statistical Society for statistical practice.

This document contains four sections: (1) a review of the study design, (2) general statistical considerations, (3) comprehensive statistical analysis methods for immunogenicity and safety outcomes, and (4) shells of proposed tables and data listings and mock figures. Within the table, figure, and listing mock-ups (Appendices 1, 2, and 3), references to CSR sections are included. Any deviation from this SAP will be described and justified in protocol amendments and/or in the CSR, as appropriate. The reader of this SAP is encouraged to also review the study protocol for details on conduct of the study and the operational aspects of clinical assessments.

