3. STUDY OBJECTIVES AND ENDPOINTS

3.1. Study Objectives

Primary Objectives:

1. Assess the safety and reactogenicity of a homologous prime boost regimen of ZPIV given at two different dose levels in a dose de-escalation format in healthy adult subjects who live in Puerto Rico, a flavivirus endemic area.
2. Compare the safety and reactogenicity profile of ZPIV after each vaccination, between dosage groups, and by pre-vaccination flavivirus immune status.

Secondary Objectives:

1. Assess the humoral immune response to a homologous prime-boost regimen of ZPIV after each dose of vaccine as determined by kinetics of the immune responses, seroconversion rates, and Geometric Mean Titers (GMT) overall, and compare results between dosage groups and by pre-vaccination flavivirus immune status.
2. Assess the durability of the humoral immune response to ZPIV at 6, 12, 18, and 24 months after the second vaccine administration overall, and compare results between dosage groups and by pre-vaccination flavivirus immune status.

Exploratory Objectives

1. Estimate the incidence of ZIKV and DENV infections between Visit 00 and the subject's last visit and describe the clinical presentation including disease severity overall, by dosage group, product received, and pre-vaccination flavivirus immune status.

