1. Number and proportion of subjects who develop an acute febrile illness (AFI) or an acute rash illness (ARI) who have evidence of acute ZIKV or DENV infection detected within 14 days of symptom onset. This endpoint will be analyzed for all subjects overall, and by dosage group, product received, and pre-vaccination flavivirus immune status.
2. Number and severity of laboratory confirmed ZIKV and DENV infections during the study, overall, by treatment group, and pre-vaccination immune status, where severity is described by:
 - Duration of symptoms
 - Grade of symptoms (mild, moderate, severe)
 - Use of concomitant medications
 - Need for hospitalization or other medical care

Laboratory confirmation will be made by AFI or ARI with either: 1) evidence of acute ZIKV and DENV infection within 14 days of symptom onset or 2) a 4-fold rise in DENV or ZIKV neutralization titers between samples collected at the last visit prior to and at the first visit following the AFI/ARI, where available.

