Venous blood and urine were collected from subjects on Day 8 and Day 15 following each vaccination for safety clinical laboratory tests. The tests include WBC, hemoglobin, hematocrit, and platelets, ALT, AST, total bilirubin, BUN, creatinine, and urine dipstick for protein and glucose. Laboratory values were assessed for adverse events according to the grading scale in [Table 7](#). Unsolicited adverse events were collected from all subjects through Day 57 (28 days after the 2nd vaccination). These events were assessed for severity and relatedness to study product. Serious adverse events (SAE), adverse events of special interest (AESI), and new onset chronic medical conditions (NOCMC) were collected for the duration of each subject's follow-up. Adverse events of special interest (AESI) for this study are neurologic and neuroinflammatory disorders collected through the duration of the subject's follow-up period.

Subjects were observed for development of an AFI/AI and all related adverse events from the time of signing the informed consent form through follow-up. Subjects who reported an ARI/AI were assessed for the following symptoms which are graded on a scale from 1 (least severe) to 3 (most severe): fever, feverishness, lethargy, restlessness, rash not at injection site, nonpurulent conjunctivitis, headache, shortness of breath, retino-orbital pain, myalgia, arthralgia, arthritis, nausea, abdominal pain, vomiting (evaluated for presence only), and bleeding (evaluated for presence only).

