9.9. Other Safety Measures

Summary tables of acute febrile illness (AFI) and acute rash illness (ARI) events will be presented. The percentage of subjects who develop ARI or AFI will be summarized by treatment group and baseline flavivirus status. Additionally, summary tables for AFI/ARI events will be presented by baseline flavivirus status.

Summaries of subjects reporting any events, any medically treated events, and any events requiring concomitant medication, including the total number of events and the number, percentage and exact 95% Clopper-Pearson CI of subjects reporting an event, will be presented for all subjects and by baseline flavivirus immune status in [Table 140](#), [Table 141](#), [Table 142](#), [Table 143](#), and [Table 144](#). Similar summaries presented by infection confirmation method are presented in [Table 147](#), [Table 148](#), [Table 149](#), [Table 150](#) and [Table 151](#).

Summaries of laboratory confirmed ZIKV and DENV infections are also presented. ZIKV and DENV infection is presented via two methods: subjects presenting with ARI/AFI and positive Arbovirus PCR result within 14 days of symptom onset or subjects presenting with ARI/AFI and a 4-fold rise in ZIKV or DENV titers following the onset of illness compared to prior to illness. The total number of laboratory confirmed ZIKV or DENV infections are summarized by treatment group, baseline flavivirus status, and confirmation method in [Table 154](#), [Table 155](#), [Table 156](#), [Table 157](#), and [Table 158](#).

The distribution of the maximum severity of symptoms of each ARI/AFI event by baseline flavivirus status and treatment group will be presented in [Table 161](#), [Table 162](#), [Table 163](#), [Table 164](#), and [Table 165](#), as well as by infection confirmation status in [Table 168](#), [Table 169](#), [Table 170](#), [Table 171](#), and [Table 172](#). For subjects reporting at least one AFI/ARI the duration of reported symptoms will be described in [Table 175](#), [Table 176](#), [Table 177](#), [Table 178](#), [Table 179](#), and by infection confirmation status in [Table 182](#), [Table 183](#), [Table 184](#), [Table 185](#), and [Table 186](#).

Individual subject listings of AFI/ARI data will be included in [Listing 12](#) (subject information), [Listing 13](#) (medical treatment sought for ARI/AI), [Listing 14](#) (ARI/AI symptoms), [Listing 15](#) (vital signs), and [Listing 16](#) (laboratory results).

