Table 138: Number and Percentage of Subjects Reporting Serious Adverse Events Related to Study Treatment by MedDRA System Organ Class, Preferred Term, Treatment Group, and Baseline Flavivirus Immune Status

Table with similar format to Table 111:

Table 139: Duration (Days) of Serious Adverse Events Related to Study Treatment by MedDRA System Organ Class, Preferred Term, Treatment Group, and Baseline Flavivirus Immune Status

Table 140: Summary of AFI/ARI Events Reported Through 12 Months Post Final Vaccination by Treatment Group – All Subjects

[Implementation note: This table can include any subjects who did not have a baseline flavivirus status observed.]

Infection Confirmation Status	2.5 mcg ZPIV (N=X)				5 mcg ZPIV (N=X)				Placebo (N=X)				All Subjects (N=X)			
	Number of Events	Number of Subjects	% of Subjects	95% CI	Number of Events	Number of Subjects	% of Subjects	95% CI	Number of Events	Number of Subjects	% of Subjects	95% CI	Number of Events	Number of Subjects	% of Subjects	95% CI
All Events	x	x	xx	x.x, x.x	x	x	xx	x.x, x.x	x	x	xx	x.x, x.x	x	x	xx	x.x, x.x
Events Requiring Concomitant Medication																
Events Requiring Medical Treatment ^a																

N = Number of subjects in the Safety population
% = percentage of subjects reporting at least one AFI/ARI event out of total number of subjects in the Safety population in the group
95% CI is calculated using the Clopper-Pearson methodology for a binomial distribution.
This table includes subjects who only received dose 1.
^aIncludes hospitalization or other medical care

Tables with similar format:

Table 141: Summary of AFI/ARI Events Reported Through 12 Months Post Final Vaccination by Treatment Group – Baseline ZIKV Seropositive Subjects

[Implementation note: If no subjects are flavivirus positive at baseline, replace this table with the following note: 'Table not generated since no positive arbovirus results were reported for ZIKV or DENV.]

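### Forty-two AFI/ARI table shells for the final analysis stop at 12 months after the last dose, although the objective and the surveillance run to the last visit

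*SAP*

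**What the plan says.** The SAP Preface describes the appended shells: "It also includes sample tables, listings, and figures planned for the final analyses". In Appendix 1, Table 140 is headed "Summary of AFI/ARI Events Reported Through 12 Months Post Final Vaccination by Treatment Group". The same 12-month limit is in the titles of Tables 141-146, 154-160, 161-167, 168-174, 175-181 and 182-188.

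The rest of the plan sets a longer window or none:

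- **Objective (SAP 3.1):** "Estimate the incidence of ZIKV and DENV infections between Visit 00 and" the subject's last visit, together with clinical presentation and severity.
- **Exploratory endpoint 2 (SAP 3.2):** "Number and severity of laboratory confirmed ZIKV and DENV infections during the study, overall, by treatment group". Severity is described by symptom duration, symptom grade, concomitant medication, and hospitalization or other care.
- **Collection (Protocol 9.4):** "AFI and ARI will be collected after signing ICF through the end of the study". SAP 4.5 agrees: "Subjects were observed for development of an AFI/AI and all related adverse events from the time of signing the informed consent form through follow-up".
- **Rationale (Protocol 2.2):** natural flavivirus infections are to be assessed for 24 months after dose 2.
- **Analysis text (SAP 9.9 and Protocol 11.4.4):** no time window is given.

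The only one-year AFI/ARI cut in the text belongs to the third interim analysis (SAP 6.2). SAP 6.2 also says that the interim analyses were governed by a separate SAP. SAP 15, which lists changes to planned analyses, does not mention a 12-month restriction.

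**The concern.** A shell title is part of the specification that programmers work from. Here it is the only place that states a window for these tables, and that window is shorter than the objective's. The restricted shells are also the only summary tables of AFI/ARI symptom severity, symptom duration, medication use and medical care, which are the four components by which endpoint 2 describes severity. If the titles are followed, year-2 illnesses would appear for these features only in subject listings, with no summary by treatment group or baseline serostatus.

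There is also a risk of inconsistent totals. Tables 147-153 count laboratory-confirmed infections with no time limit, while Tables 154-160 have confirmed-infection rows under the 12-month title. A single confirmed infection in year 2 would make the two sets differ within one report.

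**Working it through.** **Study days.** With the boost on Day 29, study day = 28 + day after second vaccination. This reproduces the protocol's own days:

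- Visit 17 (12 months): 28 + 360 = Day 388
- Visit 23 (24 months): 28 + 722 = Day 750

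**Tables affected.** The restricted layouts start at Tables 140, 154, 161, 168, 175 and 182. Each has seven versions: all subjects, two ZIKV strata and four ZIKV-by-DENV strata. So 6 × 7 = 42 tables. The one AFI/ARI layout without the limit is Tables 147-153 (7 tables).

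**Follow-up left out.** The SAP does not define the 12-month point, so several readings are shown.

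| Reading | Omitted / total days | Share |
|---|---|---|
| Cut at Visit 17, post-boost period | (750 − 388) / (750 − 29) = 362 / 721 | 50.2% |
| Cut at Day 29 + 365 = Day 394, post-boost period | (750 − 394) / 721 = 356 / 721 | 49.4% |
| Cut at Visit 17, from a Day −28 screening visit (no Day 0) | 362 / 777 | 46.6% |
| Cut at Visit 17, from a Day −1 screening visit (no Day 0) | 362 / 750 | 48.3% |
| Dose-1-only subjects, same 359-day interval from Day 1 (cut at Day 360) | (750 − 360) / (750 − 1) = 390 / 749 | 52.1% |

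The last row applies because the Table 140 footnote includes subjects who received only dose 1. On every reading about half of follow-up is left out, and six scheduled contacts (Visits 18-23) fall after the Day 388 cut.

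**Events.** The documents give no AFI/ARI rate, so the number of events lost cannot be computed. For illustration only, assume a constant yearly risk r, 90 subjects and no dropout. Expected subjects with at least one event by day t = 90 × [1 − (1 − r)^(t/365.25)].

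| Assumed yearly risk | By Day 388 | By Day 750 |
|---|---|---|
| 2% | 1.9 | 3.7 |
| 5% | 4.8 | 9.0 |
| 10% | 9.5 | 17.5 |

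**Are these interim shells left in place?** The Preface says the shells are for the final analysis. The interim report that covered one-year AFI/ARI is dated 22DEC2020 (SAP 6.2). This SAP cites protocol version 6.0 of 06 December 2021 (SAP 15), so it was written after that report. The titles were probably carried over from the interim, but that is inference.

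**Does the final analysis wait for year 2?** Yes. SAP 6.2 holds it until all safety results through Day 750 are available, and the SAP places AFI/ARI under Safety Evaluation (9.9).

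**The case against.** The strongest reply is that this is leftover wording and not an analytic choice. No section adopts a 12-month window, and no footnote or implementation note in the affected shells sets a date filter. Other shell text is visibly stale: a Table 44 footnote mentions a Group 3 that does not exist, and Table 13 gives Visit 14 as Day 290 when it is Day 209. A programmer reading SAP 9.9 might apply no filter. This is a fair account of the likely origin, and it is why the effect is stated as conditional. It does not remove the need to correct the titles, because nothing else in the SAP tells the programmer which window to use.

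The other points limit the size of the problem:

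- **Consequences.** The endpoints are exploratory and untested. Tables 147-153 keep whole-study counts of confirmed and laboratory-negative events. Listings 12-16 keep each illness in a trial of about 90 subjects. All of this stands. What would be lost is the summary by arm and serostatus of year-2 severity, duration, medication and care.
- **Table count.** SAP 9.9 cites only five tables per layout (6 × 5 = 30), and SAP 6.4 suppresses strata with fewer than two subjects. So 42 is the number of shells and an upper bound on output, and all of it comes from one repeated phrase.
- **Conflicting totals.** SAP 9.9 says "The total number of laboratory confirmed ZIKV or DENV infections are summarized by treatment group, baseline flavivirus status, and confirmation method in" Tables 154-158. By content those references look exchanged with Tables 147-151, since Table 147 is the count of confirmed infections. If so, the headline total sits in tables with no limit. Even then, Table 154 has its own confirmed-infection rows, which would differ from Table 147 if any infection occurs in year 2. The differing titles would at least label the discrepancy.

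**Conclusion.** The concern holds and should be fixed. The titles of Tables 140-146 and 154-188 contradict the exploratory objective, endpoint 2 and the collection period, and no section adopts or justifies the shorter window. If the titles are followed, about half of post-boost follow-up (362 of 721 days, 50.2%, taking 12 months as Day 388) is missing from the only summary tables of AFI/ARI severity, duration, medication and care.

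Two limits apply. The effect depends on programmers following the titles, and the number of events affected is unknown. The loss is descriptive and touches no test, primary endpoint or secondary endpoint.

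**What to change.** Retitle Tables 140-146 and 154-188, and run them, from informed consent through the subject's last study visit. State that window in one sentence in SAP 9.9.

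Define the end as the subject's last visit and not as a fixed Day 750. The protocol schedules "Visit 23, Study Day 750±14, Day 722 (24 months) Clinic Visit Following Second Vaccination", so the last visit can fall anywhere from Day 736 to Day 764. A split at 12 months may be added if the sponsor wants continuity with the interim report.

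If a 12-month restriction is intended, state and justify it in SAP 9.9 and SAP 15, and add whole-study versions of the tables. The same edit is a chance to check the SAP 9.9 references to Tables 147-151 and 154-158.

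The cost is title wording, one sentence and, if a date filter has already been programmed, its removal. The data are already collected and listed.

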4. INVESTIGATIONAL PLAN

4.1. Overall Study Design and Plan

This study is a single-center, double-blinded, placebo-controlled, Phase 1, dose de-escalation study to evaluate the safety, reactogenicity, and immunogenicity of a purified inactivated, alum-adjuvanted ZIKV vaccine (ZPIV) administered in a homologous prime-boost regimen to healthy male and non-pregnant female adult subjects living in a flavivirus-endemic area. Two dose levels will be evaluated. Each subject will receive either placebo or 5 mcg (Group 1), or 2.5 mcg (Group 2) of ZPIV administered by IM injection. The study will consist of a screening period of up to 28 days, a vaccination period in which subjects will receive a prime dose of vaccine on Day 1 followed by a homologous boost on Day 29, and a follow-up period of 24 months post boost vaccination. See [Table 1](#) of Appendix 1.

As this is a phase I study, the study will begin with enrollment of two sentinel subjects in Group 1 who will receive 5 mcg ZPIV open label. One sentinel subject will be vaccinated, followed for one day for safety and reactogenicity, and if no halting rules are met per determination of the PI and co-PI, then the second sentinel subject will receive 5 mcg ZPIV open-label. Both sentinels will be followed for safety through Day 8 and if no predefined halting rules are met and no safety concerns are identified, then enrollment of the Group 1 non-sentinel subjects will proceed in double-blind fashion. The same procedure will be used for administration of the boost vaccination to the Group 1 sentinels: 1 sentinel will receive 5 mcg ZPIV open-label, be followed for 1 day for safety and reactogenicity, and if no halting rules are met, then the second sentinel will receive the boost vaccine. Both sentinels will be followed until Day 8 after second vaccination for safety and reactogenicity and if no halting rules are then boost vaccination of the non-sentinel Group 1 subjects can proceed. Enrollment of the 2.5 mcg ZPIV group (Group 2) can begin after or at the same time non-sentinel subjects in Group 1 receive the 1st dose of vaccine.

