Table 142: Summary of AFI/ARI Events Reported Through 12 Months Post Final Vaccination by Treatment Group – Baseline ZIKV Seronegative Subjects**Table 143: Summary of AFI/ARI Events Reported Through 12 Months Post Final Vaccination by Treatment Group – Baseline ZIKV Seropositive and DENV Seropositive Subjects****Table 144: Summary of AFI/ARI Events Reported Through 12 Months Post Final Vaccination by Treatment Group – Baseline ZIKV Seropositive and DENV Seronegative Subjects****Table 145: Summary of AFI/ARI Events Reported Through 12 Months Post Final Vaccination by Treatment Group – Baseline ZIKV Seronegative and DENV Seropositive Subjects**

Table 146: Summary of AFI/ARI Events Reported Through 12 Months Post Final Vaccination by Treatment Group – Baseline ZIKV Seronegative and DENV Seronegative Subjects

Table 147: Number of Laboratory Confirmed ZIKV or DENV Infections Overall and by Confirmation Method – All Subjects

[Implementation note: This table can include any subjects who did not have a baseline flavivirus status observed.]

Infection Confirmation Status	2.5 mcg ZPIV (N=X)				5 mcg ZPIV (N=X)				Placebo (N=X)				All Subjects (N=X)			
	Number of Events	Number of Subjects	% of Subjects	95% CI	Number of Events	Number of Subjects	% of Subjects	95% CI	Number of Events	Number of Subjects	% of Subjects	95% CI	Number of Events	Number of Subjects	% of Subjects	95% CI
Positive by PCR ^a	X	X	XX	X.X, X.X	X	X	XX	X.X, X.X	X	X	XX	X.X, X.X	X	X	XX	X.X, X.X
Positive by 4-Fold Titer Rise ^b																
Any Positive Confirmation ^{a,b}																
Negative Lab Confirmation																

N = Number of subjects in the Safety Population

% = percentage of subjects reporting at least one AFI/ARI event/total number of subjects in the Safety population in the group

95% CI is calculated using the Clopper-Pearson methodology for a binomial distribution.

This table includes subjects who only received dose 1.

^a PCR confirmation includes a positive PCR result for at least one of ZIKV (blood or urine) or DENV.^b 4-fold rise in either ZIKV or DENV neutralization titers after the ARI/AFI illness visit compared to before the illness visit.^c Includes hospitalization or other medical care

Tables with similar format:

Table 148: Number of Laboratory Confirmed ZIKV or DENV Infections Overall and by Confirmation Method – Baseline ZIKV Seropositive Subjects

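### AFI/ARI and confirmed-infection percentages ignore time at risk, so subjects lost before the window ends count as event-free

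*SAP*

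**What the plan says.** Exploratory objective 1 (SAP 3.1, same in Protocol 3.1.3) is to "Estimate the incidence of ZIKV and DENV infections between Visit 00 and the subject's last visit". The period at risk therefore ends individually.

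SAP 9.9 and the Appendix 1 mock-ups set out the analysis.

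- Tables 140-146 are titled "Summary of AFI/ARI Events Reported Through 12 Months Post Final Vaccination by Treatment Group", split by baseline serostatus. Their percentage is "percentage of subjects reporting at least one AFI/ARI event out of total number of subjects in the Safety population in the group", with a Clopper-Pearson interval.
- Tables 147-153, on laboratory-confirmed infections, define theirs as "percentage of subjects reporting at least one AFI/ARI event/total number of subjects in the Safety population in the group", also with a Clopper-Pearson interval. Their titles give no window. The matching endpoint in SAP 3.2 is "Number and severity of laboratory confirmed ZIKV and DENV infections during the study". The footnote still names AFI/ARI events in the numerator, not confirmed infections.

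The Safety population (SAP 6.3.1) requires one vaccination and no minimum follow-up. SAP 4.1 plans "a follow-up period of 24 months post boost vaccination" for both groups. SAP 6.5 rules out imputation and assumes data missing completely at random. Neither SAP 9.9 nor any mock-up contains person-time, a time-to-event estimate or a summary of follow-up duration.

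**The concern.** Dividing by everyone vaccinated gives the risk over a window only if everyone is observed to the end of it. A subject who leaves early without an event stays in the denominator as a full non-event. That amounts to filling in the unobserved time as event-free, which sits badly with a plan that rules out imputation. Under the SAP's own missingness assumption, a person-time rate or Kaplan-Meier estimate handles the loss, while the crude percentage is biased downward.

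At stake is the accuracy of an exploratory estimate: how often AFI/ARI and confirmed ZIKV or DENV infection occurred. Without time at risk, the figure is also hard to set beside studies with other follow-up lengths.

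**Working it through.** **The plan's own figures.** The documents state no AFI/ARI or infection incidence and no dropout rate. The only design figures are in SAP Tables 8 and 9. They reproduce: 1 − (1 − 0.02)^80 = 80.1%, and the rate giving 80% with n = 35 is 1 − 0.20^(1/35) = 4.49%, stated as 4.5%. They do not bear on follow-up time.

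**Inputs from the documents.** The 12-month visit is Day 388 and the 24-month visit Day 750, so T = 388/365.25 = 1.062 years or 750/365.25 = 2.053 years from Day 1. Arm sizes (SAP 4.4.3) are 45 at 5 mcg, 35 at 2.5 mcg and 5 + 5 = 10 placebo.

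**Assumptions, not in the documents.** Constant hazard L from an annual risk r, with L = −ln(1 − r) and r between 2% and 20%. A share d (5% to 30%) is lost evenly over the window, unrelated to risk.

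**Formulas.**

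- Risk with full follow-up: F = 1 − e^(−LT)
- Average observed risk in leavers: E = 1 − F/(LT)
- Expected crude proportion: C = (1 − d)F + dE

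**Worked case**, r = 10%, T = 1.062, d = 10%: LT = 0.11192; F = 0.10589; E = 1 − 0.10589/0.11192 = 0.0539; C = 0.9 × 0.10589 + 0.1 × 0.0539 = 0.1007. The ratio C/F is 0.951.

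Results for r = 10%:

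| Even loss d | 12 months: crude (full 10.59%) | 24 months: crude (full 19.45%) | Ratio, 12 / 24 months |
|---|---|---|---|
| 5% | 10.33% | 18.99% | 0.975 / 0.976 |
| 10% | 10.07% | 18.52% | 0.951 / 0.952 |
| 20% | 9.55% | 17.58% | 0.902 / 0.904 |
| 30% | 9.03% | 16.64% | 0.853 / 0.855 |

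The ratio is close to 1 − d/2. Over annual risks of 2% to 20% and both windows it is 0.950-0.954 at 10% loss and 0.900-0.908 at 20%. In the extreme case where all losses fall straight after dose 1, it is 1 − d: 0.90 and 0.80.

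**Between arms.** With equal loss the ratio is the same in both arms and cancels in a relative comparison. For an identical hazard (r = 10%) and a hypothetical 5% versus 30% loss, the 12-month figures are 10.33% and 9.03%, a ratio of 0.874. Over 24 months it is 0.877.

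**Scale against sampling error.** At r = 10% and 20% even loss, the shift is 10.59 − 9.55 = 1.04 points (12 months) or 19.45 − 17.58 = 1.87 points (24 months). One subject is 1/45 = 2.2 points or 1/35 = 2.9 points. Exact 95% intervals are 2.5-21.2% for 4/45, 3.2-26.7% for 4/35 and 0.3-44.5% for 1/10.

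**The case against.** The strongest defence is that the tables deliver what was specified. Exploratory endpoint 1 (SAP 3.2) and Protocol 11.4.4 ask for a number and a proportion, and a proportion over a fixed window is an ordinary meaning of incidence. This stands as a reason to keep the crude figures. It does not remove the bias, because the proportion equals cumulative incidence only with complete follow-up, and the objective runs to each subject's own last visit.

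The defence can add that Protocol 11.4.5 expects little missing data, that SAP Tables 11 and 12 and Listing 2 show withdrawals by arm, and that no between-arm test of AFI/ARI is planned in a study not designed to test a hypothesis. All of this stands and limits the importance. Withdrawal counts alone still do not give time at risk.

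Three stronger readings are tempting, and the documents do not support them.

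- That early leavers count as infection-free for two years. Tables 140-146 stop at 12 months after final vaccination. A two-year window is possible only for Tables 147-153, where none is stated.
- That the note including dose-1-only subjects shows short follow-up. Protocol 5.3.2 and 5.3.3 separate stopping vaccination from leaving the study, and ask such subjects to remain in follow-up.
- That the hurricane made Group 1 follow-up shorter. Protocol 4 and 11.2 and SAP 5 describe lost samples in 11 subjects and delayed enrolment, not dropout. Those 11 remain in the safety analysis.

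**Conclusion.** The point holds as a low-severity weakness. Tables 140-153 ignore time at risk, so the crude percentage underestimates the incidence named in the objective whenever subjects are lost before the window ends. Under assumed even, non-informative loss and a constant hazard, the understatement is about 5% relative at 10% loss and 10% at 20%. With no loss it is zero. In the examples worked at 20% even loss, it is smaller than one subject per vaccine arm.

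A reader might infer that the arms are not comparable. That does not follow: scheduled follow-up is identical, no dropout figure is given, and distortion between arms requires a difference in retention that nothing in the documents shows.

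**What to change.** In SAP 9.9 and Tables 140-153, keep the crude n and %, which meet endpoint 1, and add by arm:

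- total person-years at risk, and first events per person-year with an exact Poisson 95% CI;
- Kaplan-Meier cumulative incidence at 12 months after the final vaccination, and also at 24 months where the table covers the whole study.

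State the start of time at risk (the objective starts at Visit 00) and the censoring date, give Tables 147-153 an explicit window, and make their percentage footnote refer to confirmed infections.

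The cost is modest programming from dates already collected: Listing 2 carries the study day of termination and Listing 12 the illness start day. The downside is wide intervals, particularly with about 10 placebo subjects and within serostatus subgroups. Both additions also rely on loss being unrelated to infection risk, which SAP 6.5 already assumes.
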